PRoVENT-IMIC: Statistical Analysis Plan

updated 20 Dic 2018

General description of statistical methods

Normally distributed variables will be expressed by their mean and standard deviation; not normally distributed variables will be expressed by their medians and interquartile ranges; categorical variables will be expressed as n (%). In test groups of continuous normally distributed variables, Student's t-test will be used. Likewise if continuous data are not normally distributed the Mann Whitney U test will be used. Categorical variables will be compared with the Chi-square test or Fisher's exact test or when appropriate as relative risks. Statistical uncertainty will be expressed by 95% confidence levels.

Time to ICU discharge will be analysed as a time to event variable using Cox proportional hazard models and visualized by Kaplan–Meier curves. Time–course variables (e.g. repeated measures of ventilatory parameters, vital signs, oxygenation parameters and others) will be analysed using mixed–effect longitudinal models with random intercepts for patients and centers; time will be treated as a continuous variable. Multiple imputation of missing values will be considered when appropriate. No correction for multiple comparisons are pre-specified, thus, all the findings should be viewed as exploratory. Statistical analyses will be conducted using R (www.r-project.org). A *P*–value of less than 0.05 will be considered statistically significant.

Baseline descriptive statistics

Patients baseline characteristics will be presented as shown in **dummy Table 1**. The predicted bodyweight of male patients will be calculated as $50+0.91(\text{height [cm]}-152.4)$ and for female patients as $45.5+0.91(\text{height [cm]}-152.4)$. Patients will be grouped based on the risk of ARDS defined as a Lung injury prediction score (LIPS) equal or greater than 4.

Analysis of the primary outcome

The primary outcomes (V_T size [ml/kg PBW] and PEEP [cm H₂O] levels during the first three days of mechanical ventilation), alike other ventilator settings – will be reported as in **dummy Table 2**. Variables that were collected daily (e.g. ventilator

parameters, respiratory rates, SpO₂) will be presented as median [IQR]. They will be analysed and compared between patients at no risk for ARDS, patients at risk for ARDS and in patients with ARDS (in case the diagnosis of ARDS could be made on admission). Also, the ventilatory variables over the first three days will be presented in line plots and the *p* value will be calculated using mixed-effect longitudinal models with random intercepts for patients and centers and an interaction between time and the risk for ARDS as fixed effect; time will be treated as a continuous variable.

Scatterplots will be used to present distributions of V_T versus PEEP, V_T versus respiratory rate, V_T versus plateau pressure and V_T versus driving pressure. Cut-offs to form matrices will be based on widely accepted values for each variable, specifically 8 ml/kg PBW for V_T , 14 breaths per minute for respiratory rate, 30 cmH₂O for plateau pressure, 5 cmH₂O for PEEP and 15 cmH₂O for driving pressure. Driving pressure will be calculated by subtracting the level of PEEP from the plateau pressure (P_{plat} in volume-control ventilation) or maximal airway pressure (P_{max} in pressure-control ventilation).

Analysis of the secondary outcomes

The number of patients developing a pulmonary complication during the first 7 days (excluding first day of mechanical ventilation) and patient outcomes at ICU discharge will be reported in absolute numbers and percentages (**dummy Table 3**).

Univariate analysis will be performed to identify potential factors associated with ICU mortality and development of pulmonary complications including, but not limited to, ventilator settings (in particular V_T and PEEP at day 0). Relevant covariates included in the final mixed-effect multivariable model will be identified as those with *p* < 0.2 in the univariable model (including participating center as a random effect), those with clinical relevance and without statistical association with other relevant variables. The linearity of each continuous predictor with the log odds outcome will be checked graphically and, if not present, a log-transformation will be performed. Pearson correlation coefficients will be used to assess collinearity between predictors. Since a high collinearity between peak, plateau and driving pressure is expected, the main model will consider the variable with the higher amount of measurements between peak or plateau pressure. Driving pressure will be considered in a sensitivity analysis, excluding PEEP, peak and plateau pressure. Finally, the intraclass correlation coefficient (ICC) will be assessed. The ICC

represents the ratio of between-site variance to total variance, ranging from 0 to 1.

Potential associations between ventilator settings and outcome will be explored in pre-specified subgroups by building a model in each category. The subgroups are: (1) patients at low risk of ARDS versus patients at risk of ARDS; (2) patients without ARDS versus patients with ARDS; (3) reason for ICU admission and (4) reason for start of invasive ventilation.

Supplementary information

- Participant ICU structure and organizational descriptives will be reported in **supplementary dummy Table 1**, aggregated per country.

Dummy Table 1. Baseline patient characteristics

	All patients (n=)	At risk of ARDS (n=)	Not at risk of ARDS (n=)	P – value
Age (years)	mean ±SD or median [IQR]	mean ±SD or median [IQR]	mean ±SD or median [IQR]	
Sex				
female	n/total (%)	n/total (%)	n/total (%)	
Country				
Thailand	n/total (%)	n/total (%)	n/total (%)	
Vietnam	n/total (%)	n/total (%)	n/total (%)	
Sri Lanka	n/total (%)	n/total (%)	n/total (%)	
Maldives	n/total (%)	n/total (%)	n/total (%)	
Bangladesh	n/total (%)	n/total (%)	n/total (%)	
Pakistan	n/total (%)	n/total (%)	n/total (%)	
India	n/total (%)	n/total (%)	n/total (%)	
Malaysia	n/total (%)	n/total (%)	n/total (%)	
Myanmar	n/total (%)	n/total (%)	n/total (%)	
Iran	n/total (%)	n/total (%)	n/total (%)	
Nepal	n/total (%)	n/total (%)	n/total (%)	
Severity of illness, SOFA score				
Total	median [IQR]	median [IQR]	median [IQR]	
Pulmonary	median [IQR]	median [IQR]	median [IQR]	
Haematological	median [IQR]	median [IQR]	median [IQR]	
Liver	median [IQR]	median [IQR]	median [IQR]	
Circulation	median [IQR]	median [IQR]	median [IQR]	
Neurology	median [IQR]	median [IQR]	median [IQR]	
Renal	median [IQR]	median [IQR]	median [IQR]	
LIPS	mean ±SD or median [IQR]	mean ±SD or median [IQR]	mean ±SD or median [IQR]	
Body mass index (kg/m²)	mean ±SD or median [IQR]	mean ±SD or median [IQR]	mean ±SD or median [IQR]	
Predicted body weight (kg)	mean ±SD or median [IQR]	mean ±SD or median [IQR]	mean ±SD or median [IQR]	
Smoker				
Never	n/total (%)	n/total (%)	n/total (%)	
Former	n/total (%)	n/total (%)	n/total (%)	
Current	n/total (%)	n/total (%)	n/total (%)	
Unknown	n/total (%)	n/total (%)	n/total (%)	
Reason for ICU admission				
Planned surgery	n/total (%)	n/total (%)	n/total (%)	
Emergency Surgery (excluding trauma)	n/total (%)	n/total (%)	n/total (%)	
Trauma	n/total (%)	n/total (%)	n/total (%)	
Medical condition	n/total (%)	n/total (%)	n/total (%)	
Non invasive ventilation before intubation				
Duration (minutes)	mean ±SD or median [IQR]	mean ±SD or median [IQR]	mean ±SD or median [IQR]	
Invasive ventilation in the ward for > 12h before ICU admission				
High risk surgery	n/total (%)	n/total (%)	n/total (%)	
Admission source				
Emergency department	n/total (%)	n/total (%)	n/total (%)	
Operating room	n/total (%)	n/total (%)	n/total (%)	
Ward	n/total (%)	n/total (%)	n/total (%)	
Directly from community	n/total (%)	n/total (%)	n/total (%)	
Reason for intubation				
Cardiac arrest	n/total (%)	n/total (%)	n/total (%)	
Anesthesia for surgery (planned)	n/total (%)	n/total (%)	n/total (%)	
Depressed level of consciousness	n/total (%)	n/total (%)	n/total (%)	
Acute respiratory failure	n/total (%)	n/total (%)	n/total (%)	
Hemodynamic instability	n/total (%)	n/total (%)	n/total (%)	
Other	n/total (%)	n/total (%)	n/total (%)	
Cause of Acute Respiratory Failure				
Community acquired pneumonia	n/total (%)	n/total (%)	n/total (%)	
Nosocomial pneumonia	n/total (%)	n/total (%)	n/total (%)	
Unplanned post operative ventilation	n/total (%)	n/total (%)	n/total (%)	
Cardiogenic pulmonary edema	n/total (%)	n/total (%)	n/total (%)	

Sepsis (other than pneumonia)	n/total (%)	n/total (%)	n/total (%)
COPD exacerbation	n/total (%)	n/total (%)	n/total (%)
ARDS	n/total (%)	n/total (%)	n/total (%)

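### The SAP names Student's equal-variance t-test for comparing LIPS risk groups and makes no provision for unequal variances; naming Welch's test would be a nearly free improvement

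*SAP*

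**What the plan says.** The rule for continuous variables is in the SAP, General description of statistical methods: "In test groups of continuous normally distributed variables, Student's t-test will be used". The alternative follows at once: "Likewise if continuous data are not normally distributed the Mann Whitney U test will be used". Neither sentence mentions equal variances, a variance check or an unequal-variance version. The same section adds "A *P*–value of less than 0.05 will be considered statistically significant" and "Statistical uncertainty will be expressed by 95% confidence levels", names R without a function or option, and declares all findings exploratory because no multiplicity correction is planned.

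The groups are defined under Baseline descriptive statistics: "Patients will be grouped based on the risk of ARDS defined as a Lung injury prediction score (LIPS) equal or greater than 4". Dummy Table 1 compares at-risk with not-at-risk patients and has a p-value column. Age, LIPS, body mass index, predicted body weight and duration of non-invasive ventilation are each to be shown as mean with SD or as median with IQR. Group counts are blank.

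PEEP, one of the two primary outcomes, is treated in two ways. Dummy Table 2 shows it as mean with SD, with a p value for each day. Under Analysis of the primary outcome, daily variables, ventilator parameters included, are to be shown as median with IQR. That section also takes the p value for the three-day course from a mixed-effect longitudinal model.

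**The concern.** Student's test estimates one common variance. When the groups differ in both size and spread, the pooled standard error is too small if the smaller group is the more variable one, and too large in the reverse case. The first gives too many false positives and intervals that are too narrow; the second gives the opposite.

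Here the groups are observed and are cut on a score of lung-injury risk, so equal spread cannot be presumed. A variable that is normal in each group but has unequal SDs still goes to Student's test under the written rule. The direction of the error cannot be known until group sizes and SDs are seen. The problem is separate from clustering by center, since it arises with fully independent patients.

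**Working it through.** **Inputs from the SAP.** Student's test for normal variables; significance at 0.05; 95% intervals; two groups split at LIPS 4. Sidedness is not stated, and two-sided is assumed. The SAP gives no sample size, SD or group ratio, so there is no figure of its own to reproduce.

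**Assumed inputs, shown as a range.** Share f of patients in the smaller group: 0.5, 0.4, 0.3 and 0.2. Ratio r = SD(smaller group) / SD(larger group): 0.5 to 2.

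**Formulas.** For N patients, N times the variance of the mean difference, in units of the larger group's variance, is:

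- true: V_true = r²/f + 1/(1 − f)
- as Student's test estimates it: V_pooled = (f·r² + 1 − f) × (1/f + 1/(1 − f))
- actual two-sided level = 2 × [1 − Φ(1.96 × k)], with k = √(V_pooled / V_true)

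N cancels from k, so a larger sample does not cure the error.

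**Worked case, f = 0.3 and r = 1.5** (for example 300 patients with SD 3 against 700 with SD 2):

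- pooled variance = 0.3 × 9 + 0.7 × 4 = 5.50
- pooled SE² = 5.50 × (1/300 + 1/700) = 0.0262
- true SE² = 9/300 + 4/700 = 0.0357
- k = √(0.0262/0.0357) = 0.856; actual level = 2 × [1 − Φ(1.678)] = 0.093; interval coverage = 90.7%

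With the larger group more variable (700 with SD 3, 300 with SD 2), the pooled variance is 0.7 × 9 + 0.3 × 4 = 7.50, pooled SE² = 0.0357, true SE² = 9/700 + 4/300 = 0.0262, k = 1.168 and the actual level is 0.022, with coverage of 97.8%.

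**Actual level at nominal 5%:**

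| Split | r = 0.5 | 0.67 | 0.8 | 1 | 1.25 | 1.5 | 2 |
|---|---|---|---|---|---|---|---|
| 50:50 | 5.0% | 5.0% | 5.0% | 5.0% | 5.0% | 5.0% | 5.0% |
| 40:60 | 2.7% | 3.4% | 4.1% | 5.0% | 6.1% | 7.0% | 8.2% |
| 30:70 | 1.2% | 2.2% | 3.2% | 5.0% | 7.3% | 9.3% | 12.5% |
| 20:80 | 0.4% | 1.3% | 2.5% | 5.0% | 8.6% | 12.1% | 17.9% |

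**Check by simulation** (normal data, N = 1000 assumed, 20,000 runs per scenario). At 30:70, Student's test rejected in 9.0% of runs at r = 1.5 and in 2.1% at r = 0.67. At 50:50 it rejected in 4.9% (r = 1.5) and 5.3% (r = 2). Welch's test stayed between 4.8% and 5.2% in all eight scenarios run.

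**The case against.** The strongest reply has four parts.

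- **No documented imbalance.** The SAP leaves every count blank and gives no SDs. Both conditions are needed, and at 40:60 with an SD ratio of 0.67 or 1.5 the level moves only to 3.4% or 7.0%. This stands: the size of the error is conditional, and it would be wrong to say that the p values fail whenever the spread differs.
- **The primary outcome.** A reader might infer that the primary analysis rests on a faulty test. The documents do not support that. Only one Dummy Table 2 row points PEEP to the t-test. The text's median and IQR points it to Mann-Whitney, tidal volume per kg predicted body weight is shown as a median even in the table, and the three-day p value comes from a mixed model. The text also plans a comparison "They will be analysed and compared between patients at no risk for ARDS, patients at risk for ARDS and in patients with ARDS", which a two-group t-test cannot supply.
- **Software.** The SAP never says pooled, and R's t.test runs Welch by default, so the analysis may turn out correct anyway. This does not repair the wording: running the default departs from the named test in its standard meaning, and following the named test leaves the error in place.
- **Limited reach.** The dummy tables have no column for a mean difference or its interval, so coverage matters only where such an interval is reported elsewhere. In Dummy Table 1 few rows are open to the t-test, each may go to Mann-Whitney instead, and the LIPS row is uninformative under any test because LIPS defines the groups. The exploratory label also lowers the stakes. All this stands. But that label is given because multiplicity is not corrected, and it does not make a single p value valid.

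**Conclusion.** The point holds as a free improvement of minor severity. The SAP names an equal-variance test for observed groups and has no provision for unequal spread. Under an assumed 30:70 split and SD ratios of 1.25 to 2, the nominal 5% becomes about 7% to 12.5% if the smaller group is more variable, and about 3% to 1% if the larger group is. With equal sizes or equal SDs it remains 5%. All splits and SD ratios are assumptions, since the SAP supplies none.

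The rows affected are those in Dummy Table 1 judged normal, such as age, body mass index and predicted body weight. The daily PEEP p values are affected only if Dummy Table 2's mean and SD takes precedence over the text. The longitudinal mixed-model results are not affected. The documents do not show that the groups are in fact unequal or that any primary result is wrong.

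**What to change.** In General description of statistical methods, replace Student's t-test by Welch's (unequal-variance) t-test, with the matching 95% confidence interval wherever a mean difference is reported. Separately, settle whether PEEP is summarised by mean and SD or by median and IQR, so that its daily test is determined.

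The cost is a few words. R's t.test already runs Welch by default, and almost no power is lost when the variances are equal.

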Pneumothorax	n/total (%)		
Pleural effusion	n/total (%)		
Atelectasis	n/total (%)		
Cardiogenic pulmonary edema	n/total (%)		
New pulmonary infiltrates	n/total (%)		
Outcome			
Death in ICU	n/total (%)		
Transferred to ward	n/total (%)		
Discharged home	n/total (%)		
Transferred to other ICU	n/total (%)		
Transferred to medium care or HDU	n/total (%)		
Palliative care	n/total (%)		
Duration of MV (days)	mean \pm SD or median [IQR]		
Length of stay in ICU	mean \pm SD or median [IQR]		
Tracheostomy	n/total (%)		

Supplementary Dummy Table 1. Participating centers characteristics, aggregated per country

Country	Country1	Country2	...Country10
Number of participating centers			
Hospital status			
Private	n/total (%)		
Public	n/total (%)		
Hospital type			
Academic	n/total (%)		
Non-academic	n/total (%)		
Type of population served			
Urban	n/total (%)		
Rural	n/total (%)		
Mixed	n/total (%)		
Type of ICU			
Surgical	n/total (%)		
Medical	n/total (%)		
Cardiothoracic	n/total (%)		
Neurological	n/total (%)		
Mixed	n/total (%)		
ICU arrangement			
Open	n/total (%)		
Closed	n/total (%)		
Total number of beds in Hospital	mean ±SD or median [IQR]		
Number of beds in ICU	mean ±SD or median [IQR]		
Total number of ICU admissions in 2017	mean ±SD or median [IQR]		
Total number of ICU admissions during the PROVENT-iMIC study period (28 days)	mean ±SD or median [IQR]		
ICUs involved in research activities	n/total (%)		
Total number of mechanical ventilators in unit	mean ±SD or median [IQR]		
Number of functioning ventilators	mean ±SD or median [IQR]		
Type of humidification mostly used			
Active humidification			
HME			
Routine use of Non Invasive Ventilation (NIV)	n/total (%)		
Availability of high flow nasal oxygen (HFNT) devices?	n/total (%)		
Dedicated physician available in ICU 24/7	n/total (%)		
Number of staff physicians per shift	median [IQR]		

Country	Country1	Country2	...Country10
Number of doctors in training or residents per shift	median [IQR]		
Number of Nurses per shift	median [IQR]		
Usual nurse to bed ratio			
1 nurse to 1 bed	n/total (%)		
1 nurse to 2 beds	n/total (%)		
1 nurse to 3 beds	n/total (%)		
1 nurse to 4 beds	n/total (%)		
Other	n/total (%)		
Availability of renal replacement therapy	n/total (%)		
Availability of pulse oximetry for all patients	n/total (%)		
Availability of end tidal CO₂	n/total (%)		
Availability of chest x-ray apparatus			
Not available	n/total (%)		
Dedicated ICU portable apparatus	n/total (%)		

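### Time to ICU discharge is planned with Kaplan–Meier curves and Cox models, with no treatment of ICU death as a competing event

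*SAP*

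**What the plan says.** The endpoint is covered by one sentence, under General description of statistical methods: "Time to ICU discharge will be analysed as a time to event variable using Cox proportional hazard models and visualized by Kaplan–Meier curves". The event is not defined further, and nothing states whether a patient who dies in the ICU is censored, counted as discharged or handled in another way. No cumulative incidence function, subdistribution model or paired cause-specific analysis appears anywhere in the SAP.

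ICU death is nevertheless an established outcome in the same document. Under Analysis of the secondary outcomes, "patient outcomes at ICU discharge will be reported in absolute numbers and percentages", and the outcome rows of Dummy Table 3 place ICU death next to transfer to the ward and discharge home. The same section says that "Univariate analysis will be performed to identify potential factors associated with ICU mortality and development of pulmonary complications"; that model works on the log-odds scale. Dummy Table 3 also has rows for "Transferred to other ICU" and for palliative care, and it reports "Length of stay in ICU" as a summary statistic.

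**The concern.** A patient who dies in the ICU can never be discharged alive, so death is a competing event. It is not ordinary censoring. The methods named leave two natural readings, and each has a flaw.

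1. **Deaths censored at the time of death.** Kaplan–Meier then treats those who died as if they could still be discharged later. Its complement overstates the probability of discharge alive whenever anyone dies, whether or not the groups differ. The Cox hazard ratio remains a valid cause-specific rate ratio for discharge, but it does not describe the chance of leaving alive.
2. **Deaths counted as discharges.** The curve correctly describes time in the ICU. The hazard ratio, however, adds the death rate to the recovery rate, so a group that dies faster can appear to leave sooner.

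The SAP's main grouping is by ARDS risk (a LIPS of 4 or more). If the Cox model compares those groups, unequal mortality is a reasonable expectation, and that is the setting in which the second reading misleads most.

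**Working it through.** **Inputs.** The SAP gives no ICU mortality, length of stay, event count or follow-up horizon for this endpoint, so there is no figure of its own to reproduce. All of the following are assumptions: constant hazards, evaluation at t = 28 days, ICU mortality m from 10% to 40%, and a total exit rate L from 0.10 to 0.20 per day.

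**Reading 1, deaths censored.**

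- True cumulative incidence of discharge alive: CIF = (1 − m)(1 − exp(−L·t))
- Complement of Kaplan–Meier: 1 − KM = 1 − exp(−(1 − m)·L·t)

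With L = 0.15, L·t = 4.2 and 1 − exp(−4.2) = 0.985:

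| ICU mortality | CIF | 1 − KM | Overstatement |
|---|---|---|---|
| 20% | 0.80 × 0.985 = 78.8% | 1 − exp(−3.36) = 96.5% | 17.7 points |
| 30% | 0.70 × 0.985 = 69.0% | 1 − exp(−2.94) = 94.7% | 25.8 points |
| 40% | 0.60 × 0.985 = 59.1% | 1 − exp(−2.52) = 92.0% | 32.9 points |

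Extremes of the assumed range:

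- L = 0.10, m = 10%: 84.5% against 92.0%, a difference of 7.4 points before rounding.
- L = 0.20, m = 40%: 59.8% against 96.5%, a difference of 36.7 points.

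A second parameterisation takes the median time to any exit as 5, 7 or 10 days, with L = ln 2 / median. At a 7-day median and 30% mortality, the CIF is 0.70 × (1 − 1/16) = 65.6% and 1 − KM is 85.6%. A simulation of 400,000 patients gave 65.7% and 85.9%. Over the three medians and mortality of 10% to 40%, the overstatement runs from 5.5 to 31.5 points.

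**Reading 2, deaths counted as discharges.** Let a be the discharge-alive hazard and d the death hazard, per day.

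- Cause-specific HR for discharge = a₁/a₀
- Any-exit HR = (a₁ + d₁)/(a₀ + d₀)
- CIF at day 28 = a/(a + d) × (1 − exp(−28(a + d)))

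| Setting (group 0; group 1) | Cause-specific HR | Any-exit HR | Discharged alive by day 28 |
|---|---|---|---|
| a 0.10, d 0.02; a 0.10, d 0.06 | 1.00 | 0.16/0.12 = 1.33 | 80% vs 62% |
| a 0.10, d 0.02; a 0.08, d 0.06 | 0.80 | 0.14/0.12 = 1.17 | 80% vs 56% |
| a 0.10, d 0.03; a 0.08, d 0.03 | 0.80 | 0.11/0.13 = 0.85 | not needed |

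A simulation of 400,000 patients per group, with follow-up ended at day 28, returned the same three pairs of hazard ratios.

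In the first row, censoring deaths would show 1 − exp(−2.8) = 94% for both groups, which hides the difference between 80% and 62%. In the second row, the any-exit hazard ratio points the opposite way from discharge alive. In the third row, with equal death hazards, the two ratios nearly agree.

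**The case against.** **The coding may be in the protocol.** Definitions of event and censoring are often placed there, and the protocol is not at hand. But the SAP itself fixes the estimators. Of the two natural codings of death, neither makes both the Kaplan–Meier curve and the Cox ratio readable as discharge alive. A third coding, keeping those who died in the risk set to the end of follow-up, would reproduce the cumulative incidence, but the SAP does not state it.

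**Each reading leaves something valid.** This is right: the Cox ratio under censoring and the curve under any exit are both sound for what they estimate. The harm comes from reading them as discharge alive, a term the SAP does not use. It is still the natural reading of a discharge curve, and the plan says nothing to prevent it.

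**The wording leans towards death as a form of discharge.** Listing death among the outcomes at ICU discharge does favour the second reading, under which the overstatements of the curve do not arise. The mixed hazard ratio then remains.

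**The reversal example is demanding.** It implies eventual ICU mortality of 0.02/0.12 = 17% against 0.06/0.14 = 43%, and the latter is above the 10% to 40% range used for the curve. With discharge hazards of 0.10 and 0.08, reversal needs a death hazard above 0.04 in the second group, that is, mortality above 0.04/0.12 = 33%. The sentence also does not name the groups or covariates for the Cox model. Reversal is therefore possible but not the general case.

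**The stakes are low.** The endpoint is not primary, deaths are tabulated and modelled separately, and the SAP says "No correction for multiple comparisons are pre-specified, thus, all the findings should be viewed as exploratory". This limits the consequence, but it repairs neither the curve nor the hazard ratio.

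**Conclusion.** The concern holds. Kaplan–Meier and Cox without a rule for ICU death are a poor choice for an endpoint that death prevents. If deaths are censored, the curve overstates discharge alive by 7 to 37 points at day 28 over exit rates of 0.10 to 0.20 per day and mortality of 10% to 40%. This needs no difference between groups. If deaths count as discharges, the hazard ratio is distorted to the extent that mortality differs: 1.33 where discharge rates are equal, 1.17 in place of 0.80 in the more extreme case, and 0.85 against 0.80 where death hazards are equal.

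These sizes rest on constant hazards and assumed rates, because the SAP supplies none; the direction of the overstatement does not. Since the endpoint is secondary to the ventilation outcomes and labelled exploratory, this is something that should be fixed, and it does not undermine the primary analysis.

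**What to change.** In General description of statistical methods, define the event as discharge alive from the ICU and name ICU death as a competing event. Replace the Kaplan–Meier curves with Aalen–Johansen cumulative incidence curves for discharge alive and for death. Report cause-specific Cox hazard ratios for both events side by side. A Fine–Gray model is optional, for use if an effect on the probability of discharge is wanted.

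The same text should state how transfer to another ICU and palliative care are coded, since both are listed outcomes and both bear on the event definition. Optionally, Dummy Table 3 could also show ICU stay and ventilation duration by ICU survival status.

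The cost is a few sentences and standard R functions, applied to data already collected. The one drawback is that two hazard ratios must be explained where one was planned.

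### A log-transformation is the only stated remedy for a non-linear predictor, so a turn in V_T or PEEP at day 0 could not be fitted and zero values have no rule

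*SAP*

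**What the plan says.** The section Analysis of the secondary outcomes describes univariable and multivariable models for "potential factors associated with ICU mortality and development of pulmonary complications", naming "ventilator settings (in particular V_T and PEEP at day 0" as the predictors of particular interest. The rule on functional form is one sentence, under which the linearity of any continuous predictor on the log-odds scale "will be checked graphically and, if not present, a log-transformation will be performed".

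Four other statements bear on the point:

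- Covariates enter the final model if p < 0.2 "in the univariable model (including participating center as a random effect"). Clinical relevance is also listed as a criterion.
- The one sensitivity analysis brings in driving pressure and takes PEEP out. It changes the predictors, not the form.
- Subgroups are examined "by building a model in each category", so the same rule carries into them.
- The V_T and PEEP bands in Dummy Table 2 and the cut-offs in Analysis of the primary outcome serve tables and scatterplot matrices, not these models. The lowest PEEP band is ≤ 5 with no lower limit. Nothing in the SAP excludes a PEEP of 0.

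**The concern.** The rule leaves two gaps.

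**Shape.** A single log term only rises or only falls. The plot may reveal a turn, but the response the SAP prescribes cannot represent one. The check triggers the inadequate step and does not guard against it. The fitted term may then show almost no association, or give the wrong direction on one side of the turn.

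**Zeros.** Log(0) does not exist. If PEEP is logged and some values are 0, the analyst must drop those patients or add a constant. The SAP does not say which, so the choice would be made with the data in view.

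At stake are the reported associations of V_T and PEEP at day 0 with ICU mortality and pulmonary complications. The primary outcomes, which describe V_T and PEEP over the first three days, are not affected.

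**Working it through.** The SAP gives no sample size, event count or effect size for these models, so there is no figure of its own to reproduce. Every numerical input below is an assumption, and the results show only what the rule does if a turn or zeros occur.

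**1. Large-sample fit of a log term to a U-shape.** Assumed: V_T ~ Normal(8, 1.8) ml/kg PBW, logit = −1.2 + b(V_T − turn)², b = ln(2)/9 (odds ratio 2 at 3 ml/kg from the turn), n = 400,000, no centre effect. Odds ratios at 5 and 11 against 8 ml/kg:

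| Turn at | True (5 / 11) | Linear term | Log term | Linear + quadratic |
|---|---|---|---|---|
| 7 | 1.26 / 3.17 | 0.61 / 1.65 | 0.63 / 1.37 | 1.28 / 3.17 |
| 8 | 2.00 / 2.00 | 0.99 / 1.01 | 1.12 / 0.92 | 2.01 / 2.00 |
| 9 | 3.17 / 1.26 | 1.62 / 0.62 | 1.93 / 0.64 | 3.17 / 1.27 |

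With the turn at 8 the association nearly vanishes. With the turn at 7 or 9, one arm gets the wrong direction. The linear term fails in the same way. The quadratic agrees closely because the data were generated from a quadratic.

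**2. Finite samples.** Assumed: V_T ~ Normal(8, 1.75) restricted to 4–14, logit = −1.2 + k(V_T − m)² with k = 0.02, 0.05, 0.10. The odds ratio at 4 ml/kg from the minimum is exp(16k) = 1.38, 2.23, 4.95 (mild, moderate, strong). The log term has a 1-df Wald test. The restricted cubic spline (knots at the 10th, 50th and 90th percentiles) has a 2-df Wald test. Results are mild/moderate/strong:

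| Scenario | Log | Spline |
|---|---|---|
| m = 8, n = 1000, p < 0.05 | 6/7/9% | 16/69/100% |
| m = 8, n = 1000, p < 0.2 | 21/22/26% | 38/87/100% |
| m = 8, 50 centres of 20, random intercept SD 0.5, p < 0.05 | 5/5/8% | 13/62/100% |
| m = 8, n = 200, p < 0.05 | 6/8/6% | 8/17/61% |
| m = 8, n = 2000, p < 0.05 | 5/6/8% | 26/93/100% |
| m = 7, n = 1000, fitted risk at 5 below that at 7 (wrong order) | 82/99/100% | 36/14/3% |

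By chance alone 20% would pass p < 0.2. In a separate set of runs for the last row, a linear term gave the wrong order in 88/100/100% against 84/99/100% for the log.

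**3. Zeros in PEEP.** With log(x + c), the step from 0 to 5 relative to the step from 5 to 10 is ln[(5+c)/c] / ln[(10+c)/(5+c)]. This is 8.98, 5.75, 3.71 and 2.96 for c = 0.01, 0.1, 0.5 and 1, so the offset is not a neutral choice.

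Next, exact large-sample logistic fits with 2, 5 or 10% at PEEP 0 and an assumed non-zero distribution (3: 3%, 4: 4%, 5: 50%, 6: 12%, 7: 4%, 8: 14%, 10: 9%, 12: 3%, 14: 1%). For the curve 0.03(x − 6)², the true odds ratio for 10 against 5 is exp[0.03(16 − 1)] = exp(0.45) = 1.57. For 0.015(x − 6)² it is exp(0.225) = 1.25.

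| True curve | True OR, 10 v 5 | Log, zeros dropped | Log(x + c), c = 0.01–1 |
|---|---|---|---|
| U, minimum at 6 | 1.57 | 1.58 | 0.83–1.06 |
| Milder U | 1.25 | 1.25 | 0.91–1.03 |
| Flat to 5, then rising | 1.57 | 1.50 | 1.02–1.28 |

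Dropping zeros does little harm here, though that result moves with the assumed distribution. Offsets attenuate the odds ratio and can reverse it only under the U-shapes.

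**4. Cost of one extra degree of freedom.** If the truth is linear, a 1-df test with 80% power has noncentrality 7.85, and on 2 df the power is 0.709. For 90% power (noncentrality 10.5) it is 0.835.

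**5. Forcing a quadratic for PEEP.** If the true effect is log-shaped (log(x + 1), scaled to OR 1.57 for 10 v 5), the fitted quadratic peaks at about 11.9, 11.3 and 11.1 cmH₂O with 2, 5 and 10% zeros and then falls, while the true curve keeps rising to the assumed maximum of 14.

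**The case against.** The strongest reply is that the harm is doubly conditional: it needs a plot that turns, or a non-linear PEEP plot together with zeros. Nothing in the SAP makes either likely. The open lower end of the ≤ 5 PEEP band is weak evidence, since the ≤ 7 V_T band is equally open and nobody expects a V_T of 0. This stands. A reader might infer that the SAP expects a U-shape or recorded zeros; it says neither.

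A reader might also infer that the log is the particular culprit. It is not, because a linear term fails alike. What remains is that the SAP looks for non-linearity and then prescribes a term that cannot express one common form of it.

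A third tempting inference is that V_T and PEEP would be dropped at the p < 0.2 screen. The SAP does not fix whether the linearity check precedes the screen, and the clinical-relevance criterion may keep both in. They could then still be kept with the wrong shape.

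On zeros, dropping them gave nearly correct odds ratios, the SAP never mentions an offset, and log(0) would be obvious to the analyst. That reduces the point to an unstated choice, which still matters because the options differ.

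Finally, the SAP says "all the findings should be viewed as exploratory". That lowers the stakes. It does not justify the rule, since exploratory work is where a shape should be allowed to show, and the SAP still applies a 0.05 threshold.

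**Conclusion.** The point holds in a limited form. The SAP's only response to non-linearity cannot represent a turn and has no rule for zeros. If the V_T or PEEP plot turns, the prescribed model can miss the association or reverse the risk order on one side. If PEEP is logged with zeros present, the odds ratio depends on how they are handled.

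The size is illustrative only. It rests on the assumed distributions, curves and sample sizes above, with no other covariates in the models. For a mild U both approaches mostly miss the association, and in a subgroup of 200 the gain is small unless the U is strong. The models are secondary and exploratory, so the importance is modest. The change is worth making because it is cheap.

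It would go too far to conclude that flexible terms should be forced for V_T and PEEP whatever the plot shows. That spends power when the relation is linear, and a forced quadratic for PEEP can create a false peak inside the data range.

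**What to change.** Keep the graphical check. In Analysis of the secondary outcomes, replace the log-transformation clause with:

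> A continuous predictor whose plot is not linear will be log-transformed only if all its values are above 0 and the plot is monotone and approximately linear on the log scale. Otherwise it will be modelled untransformed with a restricted cubic spline (3 knots at the 10th, 50th and 90th percentiles, or at distinct prespecified values if these coincide). The p < 0.2 screen will use the joint test of all terms of the predictor. The fitted curve with 95% CI will be reported, with odds ratios against 8 ml/kg PBW for V_T and 5 cmH₂O for PEEP.

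The reference values are the SAP's own scatterplot cut-offs ("5 cmH₂O for PEEP and 15 cmH₂O for driving pressure", with 8 ml/kg PBW for V_T in the same sentence) and serve only for reporting. The provision for coinciding knots is needed for PEEP. In the assumed distribution with 2% zeros, 0.02 + 0.98 × 0.07 = 8.9% of values lie at or below 4 and 0.02 + 0.98 × 0.57 = 57.9% at or below 5, so the 10th and 50th percentiles are both 5. The joint test implies that the form is settled before the screen, and the SAP should say so.

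The cost is one paragraph and standard R functions. There is one extra degree of freedom, only for predictors whose plot calls for it (80% power falls to about 71% if the truth is linear after all). The form is still chosen from the plot, as the SAP already does. The report shows a curve with odds ratios against a reference instead of a single odds ratio.
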